Examining the Effectiveness of Deep TMS in Veterans with Alcohol Use Disorder

Protocol Number: IRB-54988. NCT04927364.

Principal Investigator: [name].

Funded by: Innovator Grant from Stanford

Version: as of June 28, 2022

Brief Summary

The purpose of this study is to evaluate the efficacy of deep transcranial magnetic stimulation as a treatment for Veterans with an alcohol use disorder (AUD) to decrease the exceedingly high rate of relapse associated with this condition.

Objectives

At least 60% of those with AUD will experience a major relapse period within 6 months of treatment, irrespective of the intervention (psychosocial and/or pharmacological) employed. Consequently, the high prevalence of AUD and relapse following treatment in Veterans is associated with substantial resource allocation and costs for the VA Health Care System. Current pharmacological and psychosocial interventions demonstrate only a moderate level of efficacy, which is reflected in the high rate of relapse in AUD. TMS is a neurostimulation method that is at the forefront of innovative, non-invasive, and safe treatments for AUD, and other psychiatric disorders. To reduce the high rate of relapse in Veterans with AUD, it is necessary for interventions to more effectively address the associated neurobiological dysfunction. Non-invasive neuromodulation techniques are showing promise toward the aim of modifying specific and selective neural targets related to AUD and relapse. However, device-based interventions to date for AUD have focused on cortical stimulation. In contrast, preclinical and clinical studies, including our research team's preliminary data, suggest that subcortical nodes within the salience network could be promising novel neuromodulation targets. The dorsal anterior cingulate cortex (dACC) is a core node of the salience network, and hence the target of this proposal. Deep repetitive transcranial magnetic stimulation (dTMS) is one type of neuromodulation technique, and utilizing an H7 coil design can reach the dACC. Monitoring periodically throughout the first 6 months following treatment is crucial, given relapse within the first 6 months of treatment is robustly related to poor psychosocial functioning over the ensuing 1-3 years.

The ultimate goal of this proposal is to provide treatment that more effectively promotes sustained abstinence in the Veteran with AUD, as extended abstinence

is robustly associated with optimum biomedical, neuropsychological, psychiatric, and psychosocial recovery and functioning

Rationale for Research in Humans

The goal of this study is to evaluate the effectiveness of deep TMS applied through the established H7 coil protocol as a treatment for Veterans with an AUD; therefore, humans must be studied.

STUDY PROCEDURES

Procedures:

ALL RESEARCH ACTIVITIES WILL BE COMPLETED AT THE VA,
WITH THE EXCEPTION OF THE MRI, WHICH WILL BE DONE AT STANFORD:

Recruitment and screening: Participants will be recruited via the VA Palo Alto Addiction Treatment Services, Foundations of Recovery program.

Informed Consent: Prior to consent, The PI, Co-Is, or qualified RA, will recheck inclusion/exclusion criteria.

Baseline/Pretreatment Assessment:

- Psychiatric Assessment
- Alcohol and Substance Use assessment
- 3 Tesla Magnetic Resonance Neuroimaging
- Breathalyzer, urine test, saliva collection

Treatment Phase: Participants will receive a total of 30 deep TMS treatments, delivered 3 times per day, over 10 consecutive business days, with minor schedule variability to allow for participants' regular program scheduling at the treatment centers. Since participants will be recruited from Palo Alto VA residential treatment programs, 24-hour monitoring for any adverse events will be in place as an additional layer of participant safety. During this time, all participants will be receiving treatment as usual at the VA clinics, and scheduling of TMS will be arranged so as not to interfere with their daily curriculum.

Post-Treatment Phase: Within 3-4 days of completion of the Treatment Phase, all participants will repeat select psychiatric assessment measures, select alcohol and substance questionnaires, and 3 Tesla Magnetic Resonance Neuroimaging.

Monthly Follow-ups: For the 6 months following completion of treatments, participants will be contacted at 2-, 4-, and 6- months post-participation, via telephone or in person, to complete brief standardized measures of alcohol and substance use, as well as craving to assess for changes in these variables over the

preceding 30 days. These brief contacts will be 10-15 min in duration and tracking sobriety is the primary outcome measure of this study.

DETAILS OF RECRUITMENT, DESIGN AND TREATMENT

Recruitment and screening:

Potential participants from the VAPAHCS treatment programs will be identified based on VA medical/clinical staff diagnoses of an alcohol use disorder without any comorbid condition any conditions that be contraindicated for study (e.g., taking medications that lower seizure threshold, magnetic resonance neuroimaging contraindications, medically confirmed seizure disorder). Specifically, medical/clinical staff of the programs listed above will identify potential participants who meet eligibility criteria and inform the patient that a research opportunity is available to them and offer contact information to study personnel or the participant may request that study personnel contact them. The study has been explained to clinicians via treatment team meetings, so they are familiar with eligibility criteria. The PI, Co-Is, or qualified RA will check inclusion/exclusion criteria based on initial eligibility and sociodemographic data via in-person screen at the treatment program or at the MIRECC, Building 5, 4th floor. Private interview rooms are available for this purpose at both locations. Baseline/Pretreatment Assessment see section Innovator Grant application:

- a) Psychiatric Assessment: we will use standardized measures employed in clinical practice and research.
- b) Alcohol and Substance use: we will use standardized measures employed in clinical practice and research. Participants will be asked to submit a urine sample to screen for illegal/non-prescribed drug use and/or complete a breathalyzer to screen for alcohol use.
- c) 3 Tesla Magnetic Resonance Neuroimaging: will be conducted at Stanford University CNI.
- d) Saliva collection: Participants will be asked to provide a saliva sample for genotyping.

Design, Treatment Phase, and Treatment Arms:

This study will enroll 10 participants to receive deep TMS. Participants will receive 30 dTMS sessions over the course of 2 weeks. Participants will be required to be abstinent from alcohol and illicit substances for 7 days and demonstrate no clinically significant withdrawal symptoms prior to the pre-assessment described above.

Rationale for Brain Region Site and Technique: Converging lines of evidence support the salience network as a promising future neuromodulation target to impact treatment outcomes for AUD. However, most TMS studies to date have focused on cortical stimulation. In contrast, preclinical and clinical studies,

including our research team's preliminary data, suggest that subcortical nodes within the salience network (SN) are promising novel neuromodulation targets. Based on this evidence, our study will utilize the H7 coil to administer deep TMS to core salience network nodes. See section 3A (paragraphs 1 and 2) for a more in-depth rationale for the brain region site.

Duration of Treatment Phase: Participants will receive a total of 30 treatments over 10 consecutive days, allowing for minor scheduling variability so as not to interfere with regular program scheduling in the treatment programs. Participants will typically receive 3 treatments per day (Monday- Friday), over 2 consecutive weeks; inter-treatment interval will be at least 2 hours. Sessions will typically be conducted prior to the beginning to the participants' treatment day, and at lunch, as to not interfere with their treatment-as-usual in the VA substance treatment clinics.

Procedures for Delivery of dTMS Sessions:

- 1. Motor Threshold MT Elicitation:** Each subject will complete the motor determination procedure (MT) as outlined by the device specifications for the H7 coil.
- 2. Anatomical localization to the medial PFC and the dACC:** After MT, the TMS helmet will be positioned to the treatment location by aligning the coil to the center of the head and then moved 4 cm anterior to the optimal MT location targeting the left and right prefrontal cortex with a preference to the left medial PFC extending to the ACC.
- 3. Personalized Provocation Protocol:** Review of the literature suggest that in order to optimally modify neural networks associated with disease sites, priming prior to treatment is suggested. Current FDA cleared H7 coil protocol for OCD already implements this as standard clinical care. As such, the proposed study will develop a personalized provocation protocol for each participant that will be reviewed prior to the start of treatment in the study. During the baseline assessment, participants will meet with trained clinical study staff (i.e., clinical post-doctoral fellow or study PIs) and provided structured instruction on writing a half-page narrative describing the situation or circumstances that triggered their desire to quit. This narrative will be securely stored in order to be available for participants prior to each treatment session regardless of the treatment protocol they have been randomized. Before each dTMS treatment session, the subject will be instructed to review this personalized narrative, not to exceed 5 minutes. Once they have reached a distress level ranging from 4 - 7 on a visual analog scale, treatment pulses will be delivered.

4. **dTMS dosing:** To minimize subject discomfort, an adaptation train will be administered at the beginning of each treatment session followed by their personalized treatment parameters calculated during the MT session at the baseline visit. Device settings will be set for 100% of the subject's measured MT at a frequency of 20 Hz for 2 seconds at a time (train duration) with a 20-second intertrain interval. Each subject will receive 50 trains for a total of 2000 pulses delivered per treatment session lasting approximately 18.5 minutes per session. Each participant will receive 30 sessions totaling 60,000 pulses over the course of treatment

Post-Treatment Phase: Within 3-4 days of completion of the Treatment Phase, all participants will repeat select psychiatric assessment measures, select alcohol and substance questionnaires, random urine substance screen and alcohol breathalyzer, 3 Tesla Magnetic Resonance Neuroimaging as described above in Baseline/Pretreatment Assessment.

Monthly Follow-ups: For the 6 months following completion of the treatment phase, participants will be contacted three times (2-, 4-, and 6-months post-participation), via telephone or in person, to complete brief standardized measures of alcohol and substance use, as well as craving to assess for changes in these variables over the preceding 30 days. These brief contacts will be 15-20 min and tracking sobriety is the primary outcome measure of this study.

Procedure Risks

All procedures will be performed by staff trained specifically for the tasks for which they are responsible. All procedures, including the rTMS, and are considered low-risk procedures. rTMS is regarded as safe and without lasting side effects when established guidelines are followed. The primary serious adverse event associated with transcranial magnetic stimulation procedures are seizures, however, the estimated prevalence is very low at < 1%. In the case of transcranial magnetic stimulation-seizures, all have occurred during stimulation, there was no recurrence of seizures, and no incidences of status epilepticus. There have been no significant adverse cognitive, brain structural, neurologic or cardiovascular sequelae reported as a result of rTMS. Seizure risk will be minimized by careful patient selection by rigorously screening and exclusion of participants with history of seizure disorders or other conditions and medication use that increases risks of seizure. A seizure protocol is in place to avoid participant injury in the unlikely event that a seizure does occur attached.

The study will use the 3T UHP system at CNI. The UHP shares a common software and hardware architecture to GE's FDA-approved Premier system but uses a higher-performance gradient coil and is not FDA approved for diagnostic

use and is subject to the 21 CFR 812 investigational device(IDE) regulations as well as 21 CFR 50 and 56. The system has been tested by GE according to UL606001-1 and also for compliance with IEC 60601-2-33 (ed 3.1) - meeting limits and guidelines for peripheral nerve stimulation, patient thermal, SAR limit, acoustic noise, flammability rating UL94-5VA for safety covers, hydrostatic pressure, electrical hazards, dielectric strength and pinch point. The MRI scans in this study will also utilize operational parameters within FDA guidelines for Nonsignificant Risk thus an Investigational Device Exemption (IDE) from FDA should not be necessary. The research conducted under this protocol is not to evaluate the safety or efficacy of this device. In support of this research study, some of the image acquisition pulse sequences and post-processing software will be developed in collaboration with GE Healthcare. Any such software will be considered investigational, will function as a non-significant risk device, and is subject to the 21 CFR 812 investigational device(IDE) regulations as well as 21 CFR 50 and 56. The investigational image acquisition software will conform to FDA guidelines for MR safety related to heating (SAR), peripheral nerve stimulation (dB/dt), and acoustic noise. Overall, the risks to participants in this proposal are reasonable in relation to anticipated benefits, if any, to the participants, and the importance of the knowledge that may be expected to result.

- a. Use of Deception in the Study- N/A
- b. Use of Audio and Video Recordings-N/A

Alternative Procedures or Courses of Treatment

The participants in this study will concurrently receive standard-of care cognitive-behavioral and pharmacological interventions from the VAPAHCS substance treatment clinics they are enrolled in. There are no potential risks the participants who receive concurrent cognitive-behavioral and any procedure associated with the proposed research protocol. No participant will be enrolled who is taking a medication that lowers seizure threshold. Risks to confidentiality will be minimized by following all procedures dictated by HIPAA. Of course, potential participants may decline to be involved in the study and receive only the available standard-of-care cognitive-behavioral and pharmacological interventions.

This study will not impose any restrictions on treatment/therapy after conclusion. At this point, the dMS treatment under investigation will only be available during the treatment phase of the study.

Study Endpoint(s)

In order to have sufficient power to evaluate the primary hypotheses of this study, it is expected to continue until all participants have completed the procedures and follow-up assessments.

BACKGROUND

Past Experimental and/or Clinical Findings

To date, TMS has emerged as a promising treatment avenue for AUD and is being tested in clinical trials with some encouraging results. The traditional target of the left dorsolateral prefrontal cortex (DLPFC) suggests that targeting the DLPFC alone may be insufficient, as treated individuals resume drinking shortly after treatment at similar rates as those receiving sham. One possible explanation is the well-documented atrophy of the PFC as a result of chronic heavy drinking. Therefore, targeting a structurally compromised brain region, may not yield the most robust effect. The literature describes how TMS treatment is associated with physiological changes in the brain at the treatment target area stimulated as well as in remote brain regions connected structurally or functionally. TMS has been associated with changes in long-term potentiation (LTP) or depression (LTD) to increase neuroplasticity through increases in brain-derived neurotrophic factor (BDNF) and is implicated in influencing the excitatory/inhibitory balance of GABAergic synapses. Given the demonstrated downstream impact, novel approaches for stimulation need to occur.

An emerging advancement is the use of coils that target deeper regions of the brain and have the potential of targeting multiple, interacting brain networks. The coil configuration in this technique (and proposed in this study) stimulates a broader area (volume of stimulation is 40.3 cm^3), as well as a deeper area (subdural depth is 3cm). Through the use of this less commonly used coil type (H7), we hypothesize that we will be able to modify core nodes within the salience network that are otherwise not reached through traditional figure-of-eight coil approaches. Notably, there are only two published studies to date that utilize these H-coils for AUD, and only one focusing on the H7 coil proposed in this study. Harel and colleagues (2022) recently reported that an H7 stimulation protocol similar to the one proposed here resulted in changes in functional connectivity AND lower heavy drinking days in the active condition compared to the sham condition. However, it remains unclear if the proposed stimulation strategies will have an objectively measurable impact on their respective brain targets.

The proposed project will begin to explore if deep TMS treatments will be associated with 1) changes in task-based activation to emotional stimuli and 2)

whether these changes are associated with a reduced risk of relapse after standard VA treatment.

We believe this proposed work will provide preliminary data for a larger grant submission that could allow for a more complex study design to fully answer gaps in current knowledge about deep TMS H7 coil as a possible treatment approach for AUD.

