The mechanism of payment will adhere to the VA mandated procedure: payment form, which the participant can obtain cash or check at the VA Palo Alto upon completion of Baseline and Post-treatment Visit. This rate of compensation is commensurate with other AUD research being conducted at the VAPAHCS and the payment mechanism is used by other alcohol/substance abuse research currently conducted at the VA Palo Alto. The total amount of payment is proportional to the participant's time and effort and is intended to facilitate participation without adding undue influence.

Costs to Participants

No costs will be incurred by any participant.

Planned Duration of the Study

(i) Probable duration of study = 2.5 years.

(ii) Total time per participant:

Screening: 15 min

Baseline: 6 hours, over 1-day.

Treatment: 15 hours (Over approx 10 business days: 30 dTMS sessions, approx. 30 min each, performed 3x/day)

Post-Tx Assessment: 4 hours, over 1-day.

Follow-up assessments: 45 min (15min 3 times at 2-, 4-, and 6-months post-study)

Total Active Participation Time = approx. 26 hours over 6 months.

All procedures will be conducted before or after normal ATS clinic hours, or during lunch break, so as not to interfere with the patient's treatment schedule. The project will be conducted at the VAPAHCS MIRECC Palo Alto Division, which is on the same campus as the FOR program.

(iii). Analysis of participant data will be ongoing.

RISKS

Potential Risks

i. Risks of the Investigational devices.

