Data Monitoring Safety Board (DMSB): Reporting of Adverse Events, Adverse Device Effects, Serious Adverse Events, and Unanticipated Adverse Device Effects. Study Personnel will generate tabulations of AEs and SAEs and present a summary of these to the DMSB on a schedule set by the DMSB. The DMSB will also determine when they should be unblinded to treatment assignment for the reviewing of adverse event data. The DMSB will advise the PI concerning whether the study should continue or be stopped for safety reasons.

Communication among the Investigative Team: The PI will have a weekly group lab meeting with all RAs. Additionally, the VAPAHCS MIRECC has weekly PI meetings to discuss issues relevant to ongoing MIRECC research projects. All key VA Co-Is associated with this project attend these weekly meetings.

Study Conclusion

The experiment will end at either the normal termination or whenever the subject decides to withdraw from the study. Participants will be asked to complete the brief monthly in-person or telephone assessments as described in the follow-up phase. In the event that an interim analysis demonstrates futility, the PI, or Co-Is will determine unacceptable level of risk, regulatory agencies mandate discontinuation of the study, or a product recall occurs that necessitates stopping the study, any planned rTMS treatments will be immediately discontinued.

e. Data Safety Monitoring Plan (DSMC)

i. Data and/or events subject to review

ii. Although this study protocol is low risk, and will enroll a modest number of participants, we will create a DSMB as we believe this is consistent with best clinical practices. Types of data and events that will be reviewed are: 1) Aggregate Data Analysis Reports; 2) Progress toward Study endpoints; 3)AEs, SAEs and unanticipated problems; 4) Protocol deviations. Person(s) responsible for Data and Safety Monitoring

The Protocol Director will be the only monitoring entity for this study.

iii. Frequency of DSMB meetings-N/A

iv. Specific triggers or stopping rules

In order to have sufficient power to evaluate the primary hypotheses of this study, it is expected to continue until all participants have completed the procedures and follow-up assessments.

v. DSMB Reporting

All SAEs will be reported within 24 hours of learning of the SAE.

Unanticipated problems involving risks to participants or others will be reported within 5 days.

vi. Will the Protocol Director be the only monitoring entity?

YES

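### Three contacts two months apart, each looking back 30 days, leave about half of the 6-month follow-up outside every alcohol assessment, so 6-month relapse would be undercounted.

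*Protocol*

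**What the plan says.** Both Monthly Follow-ups paragraphs (under Study Procedures and under Details of Recruitment, Design and Treatment) set the schedule. The second states that "participants will be contacted three times (2-, 4-, and 6-months post-participation), via telephone or in person". Both say the contacts collect brief standardized measures of alcohol and substance use, together with "craving to assess for changes in these variables over the preceding 30 days", and both name the tracking of sobriety as the primary outcome. Planned Duration of the Study confirms the count: "Follow-up assessments: 45 min (15min 3 times at 2-, 4-, and 6-months post-study".

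The only other scheduled alcohol assessment after treatment is in Post-Treatment Phase: "Within 3-4 days of completion of the Treatment Phase, all participants will repeat select psychiatric assessment measures, select alcohol and substance questionnaires".

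Three other places bear on the point.
- Objectives: "Monitoring periodically throughout the first 6 months following treatment is crucial". The same section names sustained abstinence as the ultimate goal.
- Past Experimental and/or Clinical Findings sets the aim of learning whether deep TMS changes brain activation and "whether these changes are associated with a reduced risk of relapse after standard VA treatment".
- Study Conclusion uses a different frequency: "Participants will be asked to complete the brief monthly in-person or telephone assessments as described in the follow-up phase".

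**The concern.** The look-back and the schedule do not fit each other. A 30-day look-back suits six monthly calls, as the section heading and Study Conclusion suggest. Every place that gives explicit times has three calls two months apart, so every second month goes unasked. Nowhere does the protocol ask about drinking since the last contact.

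The affected variable is the primary outcome. If it is read as sobriety or relapse over the 6 months, an episode that starts and ends in a gap is lost, and one that runs on into a window may be dated late. A gap can hide drinking but cannot create it, so this error has one direction. It also misclassifies the relapse variable in the aim that links brain changes to relapse. With 10 participants in a single treatment group, each missed relapse moves the observed rate by 10 percentage points. The loss is permanent: no analysis can recover days that were never asked about.

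**Working it through.** The protocol states no coverage figure, so there is none to reproduce.

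**Inputs.** Contacts at 2, 4 and 6 months and a 30-day look-back (Monthly Follow-ups); post-treatment visit 3–4 days after the last session (Post-Treatment Phase); 6 months of follow-up. Assumption: 30-day months, so 180 days; calendar months (182.6 days) are shown as a check.

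**Coverage.** The windows are about days 31–60, 91–120 and 151–180, or 3 × 30 = 90 days.

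| Credit for post-treatment visit | Covered | Unobserved of 180 | Unobserved of 182.6 |
|---|---|---|---|
| 0 days | 90 | 90 (50.0%) | 92.6 (50.7%) |
| 3 days | 93 | 87 (48.3%) | 89.6 (49.1%) |
| 4 days | 94 | 86 (47.8%) | 88.6 (48.5%) |

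The gaps are 26–27 of the first 30 days, all of days 61–90 and all of days 121–150.

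**What this could do to a 6-month relapse rate (illustration only).** Unobserved days are not the same as missed relapses, so a model is needed. Assumptions:
- True 6-month relapse is 60%. Objectives gives at least 60%, but for a major relapse period, so it serves here only as an illustrative input.
- Each relapser has one episode of *L* days, and it is counted if any part falls in a window.
- Time to onset follows F(t) = 1 − exp(−λ(t/180)^s), with λ = −ln 0.4, so that F(180) = 0.60. Either s = 1 (constant hazard) or s = 0.6 (front-loaded).
- The post-treatment visit covers c = 3 or 4 days.

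An episode is missed if its onset lies in a gap (c to 30, 60 to 90, 120 to 150) and it ends before the gap does. Hence

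apparent relapse = 0.60 − [F(30−L) − F(c)] − [F(90−L) − F(60)] − [F(150−L) − F(120)], each bracket set to zero if negative.

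Worked case, s = 1, c = 3, L = 7: 0.600 − 0.0953 − 0.0814 − 0.0600 = 0.363.

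| Apparent relapse (true 60%) | L = 1 | L = 7 | L = 14 | L = 21 | L = 30 |
|---|---|---|---|---|---|
| s = 1, c = 3 | 30.2% | 36.3% | 43.7% | 51.3% | 60.0% |
| s = 1, c = 4 | 30.7% | 36.8% | 44.2% | 51.8% | 60.0% |
| s = 0.6, c = 3 | 29.1% | 34.4% | 41.3% | 49.4% | 60.0% |
| s = 0.6, c = 4 | 30.5% | 35.7% | 42.6% | 50.8% | 60.0% |
| Two episodes per relapser | 46.5–47.8% | 52.1–53.5% | 56.5–57.5% | 58.7–59.2% | 60.0% |

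The last row is a simulation of 1,000,000 relapsers on a whole-day grid, with a second episode starting at random in the remaining days. Its ranges span the same s and c.

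**After the change.** With a look-back to the previous contact, unobserved days fall to 0. Six monthly calls with the 30-day look-back would leave 0% (180 days) to 1.4% (182.6 days).

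**The case against.** The strongest reply is that the harm needs an endpoint the protocol does not state. Sobriety has no time frame here. Measures of change over the preceding 30 days fit repeated 30-day status at least as well as cumulative relapse, and a detailed definition may sit in an analysis plan that is not shown. Objectives speaks of periodic monitoring, which three calls provide, and the relapse aim is exploratory. This stands in part: for past-30-day abstinence at each contact there is no bias. But that endpoint does not answer the 6-month relapse question the protocol poses, and an analysis plan cannot supply data that were not collected. Periodic describes how often contact is made; three calls can still cover every day between them.

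The large losses come from short lapses that do not recur, and a rate for major relapse periods is a poor input for those. This also stands. Episodes of 30 days or more lose nothing, and with one recurrence 14-day episodes lose only about 2.5 to 3.5 percentage points, or 0.25 to 0.35 of a person among 10.

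Three smaller points are fair.
- Part of the first gap may be spent in the 28-day residential program, which would lower early risk. The program's own screening is not, however, made an outcome source.
- A participant may volunteer a relapse from a gap, but the protocol treats disclosure as a clinical matter and not as outcome data.
- Recall error could move earlier drinking into a window. The one-sided direction applies to the coverage gap alone.

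**Conclusion.** The point holds. As the schedule is written, 86 to 90 of 180 days (48–50%) lie outside every scheduled alcohol assessment. This follows from the text, with only the length of a month assumed.

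The consequence is conditional. If the primary outcome is sobriety or relapse over the full 6 months, the gaps can only lower the relapse count. The documents do not fix by how much. Under the illustration, a true 60% would appear as about 29–52% for single episodes of 1 to 21 days, about 47–59% if each relapser has a second episode, and 60% for episodes of 30 days or more. If the outcome is past-30-day abstinence at each contact, it is unbiased but is not a measure of 6-month relapse.

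This should be fixed before follow-up data are collected, because the missing days cannot be restored later.

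**What to change.** Keep the three contacts. For alcohol and substance use, replace the 30-day look-back with the period since the previous contact (since the end of treatment for the first call), recorded day by day on a calendar. Craving can keep its 30-day window. State the sobriety outcome over that continuous 6-month period; past-30-day abstinence at each contact can still be derived from the same record. Reconcile the monthly wording in the two section headings and in Study Conclusion with the 2-, 4- and 6-month schedule.

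The cost is recall over about 60 days instead of 30, which may be somewhat less accurate, and probably a few more minutes per call; the documents give no figure for either. No extra contacts or staff are needed. Call length has to be settled in any case, since it appears as 10–15 minutes and 15–20 minutes in the two Monthly Follow-ups paragraphs and as 15 minutes in Planned Duration of the Study.

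### The protocol claims sufficient power and an efficacy purpose for 10 participants, all on dTMS plus usual care, in work it elsewhere calls preliminary

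*Protocol*

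**What the plan says.** Under Study Endpoint(s), the protocol says "In order to have sufficient power to evaluate the primary hypotheses of this study, it is expected to continue until all participants have completed" all procedures and follow-up. The Data Safety Monitoring Plan repeats this under its item on triggers and stopping rules: "In order to have sufficient power to evaluate the primary hypotheses of this study". Neither place gives a power figure, significance level, effect size or test, and no hypothesis is labelled primary.

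The Brief Summary states: "The purpose of this study is to evaluate the efficacy of deep transcranial magnetic stimulation". Rationale for Research in Humans states: "The goal of this study is to evaluate the effectiveness of deep TMS". The title also speaks of effectiveness. On the outcome, both Monthly Follow-ups sections say "tracking sobriety is the primary outcome measure of this study". The only reference rate is in Objectives: "At least 60% of those with AUD will experience a major relapse period within 6 months of treatment".

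On the design, Design, Treatment Phase, and Treatment Arms says "This study will enroll 10 participants to receive deep TMS". Planned Enrollment gives the same number, drawn from a 28-day residential programme. Under Alternative Procedures or Courses of Treatment, participants "will concurrently receive standard-of care cognitive-behavioral and pharmacological interventions".

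Past Experimental and/or Clinical Findings presents the project as a first exploration of two things: task-based activation change, and its association with relapse. It says the results will feed a larger grant application. It also contains the document's one explicit hypothesis, that the H7 coil can modify core salience-network nodes. Benefits calls the study preliminary and a basis for later, larger work.

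**The concern.** The same 10 participants are described in two incompatible ways: as a study whose completion secures adequate power to evaluate efficacy, and as a preliminary exploration. The design fits only the second description.

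The wording matters when results are written up. Under the first description, a low relapse count could be reported as an adequately powered efficacy success, and a count near the reference rate as evidence that dTMS does not work. Ten participants without a comparator support neither statement. Benefits expects the findings to be disseminated and to shape a larger study, so a misreading would carry forward.

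**Working it through.** **What can be reproduced.** Nothing numerical: the protocol gives no power calculation to rebuild. What follows is an illustration under stated assumptions.

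**Inputs from the protocol.** n = 10, one treatment, follow-up to 6 months, sobriety as the primary outcome, and a reference relapse rate of at least 60%. Ten is a ceiling, because Procedures to Minimize Risk provides for withdrawals during treatment.

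**Assumptions.** Relapse is binary at 6 months; all 10 are counted; the test is a two-sided 5% exact binomial test against a fixed null p0; 80% is taken as adequate power. Because the reference is a lower bound, p0 runs from 60% to 75%. Two common exact p-values are used: minimum likelihood, and the doubled one-sided p.

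**1. Sobriety against a 60% null.** With X the number of relapses, X ~ Bin(10, p0).
- P(X ≤ 2) = 0.0123; two-sided 0.0183 (minimum likelihood) or 2 × 0.0123 = 0.0246 (doubled).
- P(X ≤ 3) = 0.0548; two-sided 0.101 or 2 × 0.0548 = 0.110.
- So at most 2 relapses in 10 are needed under either method.
- Power = P(X ≤ 2 | true rate) = 0.167, 0.383 and 0.678 at true relapse of 40%, 30% and 20%.
- Power reaches 0.80 at a true rate of 15.8%, a fall of 60 − 15.8 = 44.2 points.

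**2. Other nulls.** The true rate giving 80% power depends only on the cutoff: 15.8% for 2 or fewer, 23.9% for 3 or fewer, 32.7% for 4 or fewer.

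| Null | p-value method | Cutoff | Fall needed (points) |
|---|---|---|---|
| 60% | both | 2 | 60 − 15.8 = 44.2 |
| 62% | minimum likelihood | 3 | 62 − 23.9 = 38.1 |
| 65% | minimum likelihood | 3 | 65 − 23.9 = 41.1 |
| 65% | doubled | 2 | 65 − 15.8 = 49.2 |
| 70% | both | 3 | 70 − 23.9 = 46.1 |
| 71% | minimum likelihood | 4 | 71 − 32.7 = 38.3 |
| 73.7% | doubled | 3 | 73.7 − 23.9 = 49.8 |
| 75% | both | 4 | 75 − 32.7 = 42.3 |

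The cutoff jumps between round values, so the null was stepped through in 0.1-point increments. Minimum likelihood gives about 38 to 47 points and the doubled p about 41 to 50. Overall the range is about 38 to 50.

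**3. What an observed count would settle.** At 3/10 relapses the exact 95% interval is 7% to 65%, which still includes 60%. The highest count whose interval lies wholly below 60% is 2/10 (3% to 56%).

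**4. Activation change by relapse status.** Two-group t test, 8 degrees of freedom, noncentrality d√(n1·n2/(n1+n2)). Power of 80% needs d of about 2.0 (5 v 5), 2.1 (6 v 4), 2.2 (7 v 3) or 2.5 (8 v 2).

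**5. Pre-post change in activation.** Paired t test, 9 degrees of freedom, noncentrality d√10. Power is 29%, 62% and 80% at d = 0.5, 0.8 and 1.0.

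**6. Attribution.** Every participant receives dTMS and concurrent cognitive-behavioural and pharmacological care. No untreated or sham group is described. A relapse rate from this design reflects both together, and a larger n would not separate them.

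**The case against.** **The sentence only says the study will not stop early.** It does sit under endpoint and stopping-rule headings, and it gives no figure. But the reason it offers for continuing is that completion provides sufficient power, so the claim remains.

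**The power figures rest on an analysis that the protocol does not fix.** This stands. Follow-up collects repeated alcohol-use and craving measures at 2, 4 and 6 months, each covering the preceding 30 days. A repeated or continuous sobriety analysis would have different power. The 38 to 50 points illustrate one plausible analysis; they are not a property of the trial.

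**The only explicit hypothesis is mechanistic.** This stands in part. A within-person change can be detected without a comparison group, and d of about 1.0 suffices for 80% power. A reader might infer that nothing in the study is adequately powered; the document does not support that. Still, the sentence speaks of hypotheses in the plural, and the stated primary outcome is sobriety.

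**The preliminary nature is disclosed.** It is, in Background and Benefits, and that limits the harm. It is also what the power and efficacy wording contradicts.

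**The study may not be single-arm.** Wording on randomised protocols, SAE collection from randomisation, and unblinding of the monitoring board appears in the Personalized Provocation Protocol and the adverse-event sections. A reader might infer a control arm, but none is described, and both statements of enrolment support one treatment for all 10.

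**The protocol disclaims evaluating efficacy.** The sentence under Procedure Risks that says so concerns the MRI scanner, not dTMS.

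**Conclusion.** The point holds as a conflict of wording, and that conflict needs no calculation: claims of sufficient power and an efficacy purpose sit beside 10 participants, no comparator, concurrent care and a preliminary description.

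Its size depends on which hypothesis is meant. For sobriety as binary 6-month relapse, under the assumptions listed, 80% power needs a fall of about 38 to 50 percentage points, varying with the null and the p-value method. The activation-relapse association needs d of about 2.0 to 2.5. The pre-post activation change needs about 1.0 and is less affected. Attribution of sobriety to dTMS fails at any sample size.

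A reader might go further and infer that the design is invalid or that a sample-size rationale is missing. Neither is supported. A single-arm pilot is a legitimate choice, and a rationale may sit in a statistical analysis plan that was not available. The change is worth making because the overclaim is repeated and cheap to correct.

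**What to change.** Under Study Endpoint(s) and in the stopping-rules item of the Data Safety Monitoring Plan, delete the opening clause about power and keep the remainder, that the study runs until everyone has finished procedures and follow-up. Add a sentence such as: *Ten participants form a preliminary sample that is not powered to establish efficacy on sobriety or relapse, which will be reported as an estimate with a 95% confidence interval.*

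In the Brief Summary and Rationale for Research in Humans, reword the purpose as preliminary estimation of outcomes during dTMS plus usual residential care, consistent with Background and Benefits, and align the title. Leave all safety provisions unchanged.

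The cost is protocol wording only, with no added participants, visits or procedures. The downside is a more modest stated claim.
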